APPENDIX: B - TRANSTHORACIC ECHOCARDIOGRAM (TTE) PROTOCOL

With the subjects in the left lateral position, standard transthoracic imaging should be obtained in the parasternal long-axis, parasternal short-axis, apical 4-chamber, apical 2-chamber and apical 3-chamber views. For the evaluation of left ventricular systolic function a sweep of the entire chamber from base to apex should be imaged from the parasternal short axis view. Evaluation of all 4 valves should include color flow Doppler, continuous and pulse wave Doppler interrogation. With the subjects lying supine, the atrial septum should be evaluated in the subcostal long axis view by both 2D imaging alone and with color flow Doppler.

Any post procedure complication such as pericardial effusion must be documented.

APPENDIX: C - AMERICAN HEART ASSOCIATION RECOMMENDATIONS FOR PROPHYLAXIS

PREVENTION OF INFECTIVE (BACTERIAL) ENDOCARDITIS Wallet Card

This wallet card is to be given to patients (or parents) by their physician. Healthcare professionals: Please see back of card for reference to the complete statement.

Name: _____ needs protection from INFECTIVE (BACTERIAL) ENDOCARDITIS because of an existing heart condition.
Diagnosis: _____
Prescribed by: _____
Date: _____

You received this wallet card because you are at increased risk for developing adverse outcomes from infective endocarditis (IE), also known as bacterial endocarditis (BE). The guidelines for prevention of IE shown in this card are substantially different from previously published guidelines. This card replaces the previous card that was based on guidelines published in 1997.

The American Heart Association's Endocarditis Committee together with national and international experts on IE extensively reviewed published studies in order to determine whether dental, gastrointestinal (GI), or genitourinary (GU) tract procedures are possible causes of IE. These experts determined that there is no conclusive evidence that links dental, GI, or GU tract procedures with the development of IE.

The current practice of giving patients antibiotics prior to a dental procedure is no longer recommended **EXCEPT** for patients with the highest risk of adverse outcomes resulting from IE (see below on this card). The Committee cannot exclude the possibility that an exceedingly small number of cases, if any, of IE may be prevented by antibiotic prophylaxis prior to a dental procedure. If such benefit from prophylaxis exists, it should be reserved **ONLY** for those patients listed below. The Committee recognizes the importance of good oral and dental health and regular visits to the dentist for patients at risk of IE.

The Committee no longer recommends administering antibiotics solely to prevent IE in patients who undergo a GI or GU tract procedure.

Changes in these guidelines do not change the fact that your cardiac condition puts you at increased risk for developing endocarditis. If you develop signs or symptoms of endocarditis—such as unexplained fever—see your doctor right away. If blood cultures are necessary (to determine if endocarditis is present), it is important for your doctor to obtain these cultures and other relevant tests **BEFORE** antibiotics are started.

Antibiotic prophylaxis with dental procedures is reasonable only for patients with cardiac conditions associated with the highest risk of adverse outcomes from endocarditis, including:

- Prosthetic cardiac valve or prosthetic material used in valve repair
- Previous endocarditis
- Congenital heart disease only in the following categories:
 - Unrepaired cyanotic congenital heart disease, including those with palliative shunts and conduits
 - Completely repaired congenital heart disease with prosthetic material or device, whether placed by surgery or catheter intervention, during the first six months after the procedure*
 - Repaired congenital heart disease with residual defects at the site or adjacent to the site of a prosthetic patch or prosthetic device (which inhibit endothelialization)
- Cardiac transplantation recipients with cardiac valvular disease

*Prophylaxis is reasonable because endothelialization of prosthetic material occurs within six months after the procedure.

Dental procedures for which prophylaxis is reasonable in patients with cardiac conditions listed above.

All dental procedures that involve manipulation of gingival tissue or the periapical region of teeth, or perforation of the oral mucosa*

***Antibiotic prophylaxis is NOT recommended for the following dental procedures or events:** routine anesthetic injections through noninfected tissue; taking dental radiographs; placement of removable prosthodontic or orthodontic appliances; adjustment of orthodontic appliances; placement of orthodontic brackets; and shedding of deciduous teeth and bleeding from trauma to the lips or oral mucosa.

**Antibiotic Prophylactic Regimens
for Dental Procedures**

Situation	Agent	Regimen—Single Dose 30-60 minutes before procedure	
		Adults	Children
Oral	Amoxicillin	2 g	50 mg/kg
Unable to take oral medication	Ampicillin OR	2 g IM or IV*	50 mg/kg IM or IV
	Cefazolin or ceftriaxone	1 g IM or IV	50 mg/kg IM or IV
Allergic to penicillins or ampicillin— Oral regimen	Cephalexin**†	2 g	50 mg/kg
	OR		
	Clindamycin	600 mg	20 mg/kg
	OR		
	Azithromycin or clarithromycin	500 mg	15 mg/kg
Allergic to penicillins or ampicillin and unable to take oral medication	Cefazolin or ceftriaxone†	1 g IM or IV	50 mg/kg IM or IV
	OR Clindamycin	600 mg IM or IV	20 mg/kg IM or IV

*IM—intramuscular; IV—intravenous

**Or other first or second generation oral cephalosporin in equivalent adult or pediatric dosage.

†Cephalosporins should not be used in an individual with a history of anaphylaxis, angioedema or urticaria with penicillins or ampicillin.

Gastrointestinal/Genitourinary Procedures: Antibiotic prophylaxis solely to prevent IE is no longer recommended for patients who undergo a GI or GU tract procedure, including patients with the highest risk of adverse outcomes due to IE.

Other Procedures: Procedures involving the respiratory tract or infected skin, tissues just under the skin, or musculoskeletal tissue for which prophylaxis is reasonable are discussed in the updated document (reference below).

Adapted from *Prevention of Infective Endocarditis: Guidelines From the American Heart Association*, by the Committee on Rheumatic Fever, Endocarditis, and Kawasaki Disease. *Circulation*, 2007; 116: 1736-1754. Accessible at <http://circ.ahajournals.org/cgi/reprint/CIRCULATIONAHA.106.183095>.

Healthcare Professionals—Please refer to these recommendations for more complete information as to which patients and which procedures need prophylaxis.

The Council on Scientific Affairs of the American Dental Association has approved this statement as it relates to dentistry.

National Center
[name]
[name]
americanheart.org

© 2008, American Heart Association.
All Rights Reserved. Lithographed in Canada.

50-1605 0805

APPENDIX: D- CLINICAL INVESTIGATIONAL PLAN CHANGES DUE TO ENROLLMENT DISCONTINUATION

AGA Medical/St. Jude Medical has made the decision to discontinue further enrollments in the AMPLATZER Cardiac Plug (ACP) IDE trial. This decision was not a consequence of a safety or efficacy issue with the device or the study. All device subjects should continue to be followed per the protocol with the modifications noted below.

The following sections of the protocol are being changed due to the discontinuation of enrollment in the trial.

1.5 DURATION OF THE INVESTIGATION AND SAMPLE SIZE

A total of 97 subjects were enrolled in the trial at 17 centers. Safety data collected will be summarized in a final report. No additional subjects or centers will be added to the study.

2.12 FOLLOW-UP REQUIREMENTS

#3 From: For subjects randomized to control arm and those subjects who are randomized to device arm but do not undergo an implant attempt, follow-up windows are calculated based on the day of randomization. For subjects who undergo an implant attempt and/or receive the device, follow-up windows are calculated from the date of procedure. Subjects who are on warfarin should maintain an INR between 2-3 INR levels must be documented on an INR log.

To: Control subjects should be discontinued (exited) from the trial.

To: Device subjects who underwent an implant attempt, however did not receive the ACP device, should be discontinued (exited) from the trial.

To: Device subjects will have office visits through 2-years post-implant, and then telephone visits annually through 5 years post-implant. Once the subject has completed the 5 year telephone follow-up visit they should be discontinued (exited) from the trial.

#10 From: As part of the health economic and quality of life sub-study, hospital bills of enrolled subjects will be collected up to 2 years or until the study is completed.

To: The health economic and quality of life sub-study is being stopped. The collection of hospital bills is discontinued. The hospital bills collected for the index procedure will be analyzed.

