2.12 FOLLOW-UP REQUIREMENTS (REFER TO APPENDIX D)

1. Refer to section 2.12.1, 2.12.2, and 2.12.3.
2. Adverse events for all randomized subjects will be collected from the time of informed consent through discontinuation or end of the study.
3. For subjects randomized to control arm and those subjects who are randomized to device arm but do not undergo an implant attempt, follow-up windows are calculated based on the day of randomization. For subjects who undergo an implant attempt and/or receive the device, follow-up windows are calculated from the date of procedure. Subjects who are on warfarin should maintain an INR between 2-3 INR levels must be documented on an INR log. (REFER TO APPENDIX D)
4. Post procedure TEE requirements for the device arm subsequent to hospital discharge: Refer to TEE flow chart below.
5. For subjects randomized to the device arm, once OAC therapy is discontinued, aspirin (325 mg daily) must be started and continued throughout the duration of the trial. If the subject is already on aspirin 81 mg daily, increase dosage to 325 mg daily.
6. Bacterial endocarditis prophylaxis should be carried out for at least six months post procedure (see Appendix C).
7. For subjects who receive the device, a telephone call must be scheduled 3 months (+/- 10 days) post discontinuation of OAC therapy to inquire if subjects have restarted OAC therapy. Telephone call will be documented as an Interim Visit.
8. If during a phone follow-up, a serious adverse event is reported or a response of “Yes” or “Don’t know” to any question on Neurological Symptom Interview is elicited, an in-person interim office visit is required.
9. If asymptomatic cerebral hemorrhage is detected through imaging, please note that there are no standardized clinical guidelines or treatment recommendation for the use of antithrombotic therapy based on MR Imaging findings. These subjects in both groups (device and medical management) should be managed per institutional or investigator standard of care.
10. As part of the health economic and quality of life sub-study, hospital bills of enrolled subjects will be collected up to 2 years or until the study is completed. (REFER TO APPENDIX D)

Transesophageal Echocardiogram (TEE) Imaging Schedule
Flow Diagram for Subjects who are randomized to the device arm

2.12.1 ASSESSMENT AND FOLLOW-UP SCHEDULE; SUBJECTS WHO RECEIVE THE DEVICE (REFER TO APPENDIX D)

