2.15.1 Feasibility Subset

The first 30 subjects who receive the ACP device (plus any subjects with device implant attempts), will compose the feasibility subset. The primary aim of this subset is to assess the incidence of serious adverse events (SAE) in the first 45 days after procedure. The 45-day SAE and TEE data for these first 30 device subjects will be submitted to the FDA. Enrollment will halt while the 30 day safety data are collected, analyzed, and submitted to FDA for review, although follow-up will continue among the device and control subjects already enrolled in the trial. The DSMB and/or CEC will also review this data prior to submission.

The date of the first attempted implant procedure will determine the subjects that qualify for this group. Since it may be difficult to determine which subject had the 30th ACP implant procedure, any subject with the same initial procedure date as another subject in this group will be reported among the feasibility group. This may increase the feasibility sample size beyond 30 subjects. In addition, subjects with an attempted, but not implanted device will be analyzed in this group but will not count towards the limit of 30; this may also increase the sample size beyond 30 subjects.

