2.15.8.1 Per Protocol Analysis

a. This analysis does not count subjects who did not follow the protocol.

This cohort is defined as all subjects who:

- Receive the device (for subjects in the device arm) or were randomized to receive the device but did not receive the device due to a procedural adverse event or adverse event related to the pre-procedural termination of warfarin or dabigatran, such as ischemic stroke or thrombus observed in the left atrium/atrial appendage at or prior to the implant procedure.
- As directed by the protocol, discontinue OMT (for subjects in the device arm) given the absence of flow or a minimal flow of ≤ 3 mm into the LAA, as demonstrated by TEE, or continue OMT due to more than minimal flow present on TEE.
- Are started on and comply with warfarin or dabigatran use (device and control arms).
- Achieve and maintain a therapeutic INR (subjects in device and control arms who are on warfarin therapy). Have at least monthly monitoring with at least 70% of visits made and 60% time in therapeutic range (INR 2.0-3.0).

Subjects (device and control arms) who switch to an alternative anticoagulant approved for the treatment of atrial fibrillation other than warfarin or dabigatran will be excluded from this analysis.

b. Assessment of Proof of Concept: This analysis will be conducted to assess outcomes in subjects who receive the ACP device and follow the protocol-mandated post implant medication regimen compared to subjects treated appropriately with warfarin or dabigatran. This analysis does not count subjects who are randomized to device but do not receive a device, device subjects with LAA closure who fail to stop warfarin or dabigatran at day 45, and all subjects) who deviate from therapeutic warfarin administration and monitoring (For device subjects this is from day of procedure to day 45 and for control subjects it is from day of randomization onward).

This cohort is defined as:

- Receive the device (for subjects in the device arm).
- As directed by the protocol, discontinue warfarin or dabigatran (for subjects in the device arm) given the absence of flow or a minimal flow of ≤ 3 mm into the LAA, as demonstrated by TEE.
- Are started on and comply with warfarin or dabigatran use (device and control arms).
- Achieve and maintain a therapeutic INR (for subjects on warfarin in device and control arms). At least monthly monitoring with at least 70% of visits made and 60% time in therapeutic range (INR 2.0-3.0).

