2.15.3 Study Design

The study as designed was intended to determine the difference in efficacy and safety between the device and control arm (subjects treated with OMT).

There were three primary endpoints and hypotheses intended to be evaluated in the ACP clinical trial; these will no longer be analyzed as specified in the original trial protocol, rather, will be summarized as below:

1. From: An efficacy endpoint which compares the 2-year event rates of ischemic stroke and peripheral thromboembolism. This is a non-inferiority analysis where the device will be deemed efficacious if the risk ratio is < 1.75 or the risk difference in two years event rates is < 2.87 .

To: This objective will not be analyzed as specified above. A summary of ischemic strokes and peripheral thromboembolism reported through 2 years of follow-up will be provided using descriptive statistics.

2. From: A long-term safety endpoint which compares long-term composite rates of all-cause mortality and major bleed. This is a superiority analysis where the

device will be deemed safe if the safety event rate in the device arm is proven superior to the safety event rate in the control arm (OMT).

To: This objective will not be analyzed as specified above. A summary of all-cause mortality and major bleeds reported through 2 years of follow-up will be provided using descriptive statistics.

3. From: An acute safety (short-term) endpoint which compares the rate of device or procedure related serious adverse events against a performance goal (PG). If this rate is less than 5%, the device is considered to have met the acute safety endpoint.

To: This objective will not be analyzed as specified. A summary of the device or procedure related serious adverse events reported through hospital discharge will be provided using descriptive statistics.

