2.15.7 Primary Analysis

From: Intent-to-treat analysis- Subjects are considered enrolled in the ACP clinical trial after informed consent and HIPAA authorization form or any other applicable permission form required by law has been signed and the subject has been randomized. All primary endpoint analyses will be based on the “intent-to-treat” principle. Specifically, subjects will be considered part of the intent-to-treat analysis population as long as they are randomized into the study, with no adjustment made for whether the device was implanted, compliance with treatment, or events occurring after randomization.

To: All device subjects will be summarized in a final report. Descriptive statistics will be used to summarize the analysis of all primary endpoints.

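### Does the loose use of 'device subjects' in Appendix D let events that prevented implantation drop out of the final safety summaries?

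*Combined protocol and SAP*

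**What the plan says.** Appendix D amends the protocol after enrollment was discontinued. Its opening paragraph keeps all device subjects in follow-up, subject to the changes listed after it. Under 2.12 #3, control subjects exit; then "Device subjects who underwent an implant attempt, however did not receive the ACP device, should be discontinued (exited) from the trial"; then "Device subjects will have office visits through 2-years post-implant, and then telephone visits annually through 5 years post-implant".

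Appendix D 2.15.7 replaces the intent-to-treat paragraph with "All device subjects will be summarized in a final report", the primary endpoints being summarized descriptively. Appendix D 2.15.3 withdraws the three hypotheses and keeps three descriptive summaries. Item 3, on acute safety, reads "A summary of the device or procedure related serious adverse events reported through hospital discharge will be provided using descriptive statistics". Item 1, on effectiveness, reads "A summary of ischemic strokes and peripheral thromboembolism reported through 2 years of follow-up will be provided using descriptive statistics". Item 2 does the same for death and major bleeding. None of the three names a population or a denominator.

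Three places in the main body bear on the point. The per-protocol definition in 2.15.8.1 (an analysis Appendix D cancels) recognizes device-arm subjects who "did not receive the device due to a procedural adverse event or adverse event related to the pre-procedural termination of warfarin or dabigatran". In the feasibility subset (2.15.1), "subjects with an attempted, but not implanted device will be analyzed in this group but will not count towards the limit of 30". And 2.12 item 2, which Appendix D leaves alone, says "Adverse events for all randomized subjects will be collected from the time of informed consent through discontinuation or end of the study".

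**The concern.** Two consecutive instructions in Appendix D 2.12 #3 seem to use one term for two groups. The first applies 'device subjects' to people who never received the plug; the second gives 'device subjects' an implant date, which only recipients have. The report population in 2.15.7 then rests on that term.

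If recipients only were meant, the loss would not be random. A procedural event can be the reason no device was implanted, so restricting the summary to recipients would remove such events because of the outcome itself. The event count could then only stay the same or fall. The replaced 2.15.7 text ruled this out by including everyone randomized, implanted or not. Appendix D also cancels the outputs that might have shown the same events elsewhere: the secondary endpoints, the per-protocol and as-treated analyses, and the adverse event categorization. The descriptive summaries are the only primary-endpoint output left.

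**Working it through.** **1. Which sense fits the text.**

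- *Recipients only.* The exit instruction would then concern recipients who did not receive the device, which is a contradiction in terms. This sense fails.
- *Device arm.* The exit instruction is an exception, and the visit instruction that follows covers those who remain. The opening paragraph of Appendix D fits as well, because the exit is one of the modifications it announces. In 2.15.7, all device subjects is then the device arm: the intent-to-treat population less the controls, who have exited.

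One sense therefore carries both sentences. Main-body usage is mixed. The opening of 2.15 counts implant attempts in addition to device subjects, so it means recipients. The headings under 2.11.4.2 use the term for subjects without a device. The main body does not settle the matter alone, but it does not contradict the device-arm reading.

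**2. Whether an event that stopped an implant is reported.**

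- Section 1.4.2.1 (repeated in 2.15.3.4 and 2.15.5.2.1) sets the acute endpoint in the device arm from randomization to discharge. Appendix D lists the sections it changes, and 1.4 is not among them. Its 2.15.3 item 3 drops the comparison with the performance goal and names no narrower group.
- Section 2.7, also unlisted, counts randomized subjects in the primary endpoint analysis whether or not a device was implanted.
- Appendix D 1.5 says the collected safety data will be summarized, with no limit to recipients.
- Appendix D 2.16.2 keeps the DSMB adjudicating all adverse events.
- A serious event that aborts an implant is procedure related and occurs before discharge, so it meets item 3 as written. Exit ends future visits; it does not erase events already recorded under 2.12 item 2.

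Stroke is not one of the five listed acute components. A stroke after anticoagulation was stopped for the procedure belongs mainly to the item 1 summary.

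**3. How far the reading could move a figure.** The documents give no counts by arm or implant status, so this is illustration only.

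The plan's own acute figure reproduces from Table 3: 0.05 + 0.22 + 2.97 + 0.46 + 1.23 = 4.93%, rounded there to a 5% goal.

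- Device arm: 97 enrolled (Appendix D 1.5) at 2:1 (2.10): 97 × 2/3 = 64.7, about 65.
- Without a device: 9%, the immediate-crossover share in the as-treated simulations (2.15.5.3.3), used as a stand-in: 65 × 0.09 = 5.85, about 6, leaving 59 recipients.
- Acute events: 65 × 0.05 = 3.25, or 65 × 0.0493 = 3.20; take 3.

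Whole device arm: 3/65 = 4.6% (exact 95% interval 1.0 to 12.9%). Recipients only:

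| Events in non-recipients | 2 without device (63) | 6 without device (59) | 8 without device (57) |
|---|---|---|---|
| 0 | 3/63 = 4.8% | 3/59 = 5.1% | 3/57 = 5.3% |
| 1 | 2/63 = 3.2% | 2/59 = 3.4% | 2/57 = 3.5% |
| 2 | 1/63 = 1.6% | 1/59 = 1.7% | 1/57 = 1.8% |
| 3 | not possible | 0/59 = 0% | 0/57 = 0% |

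The exact interval for 2/59 is 0.4 to 11.7%, which overlaps almost wholly with that for 3/65.

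Two-year effectiveness, at the planned 2.95%: 65 × 0.0295 = 1.92, about 2 events. Whole arm 2/65 = 3.1%. Recipients only 2/59 = 3.4%, or 1/59 = 1.7% if one event was in an exited subject.

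**The case for a change.** The strongest reply is that a natural reading is not a specification. The one paragraph that expressly protected non-recipients in the analysis section was struck out and replaced by an undefined term. Section 2.7 cannot simply govern in its place, because it also covers controls, whom the new 2.15.7 leaves out. If the choice of population is left to the report stage, it is made with the events already known, and the table above shows that it could change an acute rate severalfold. The remedy would be cheap, because the data are already collected.

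Part of this stands. Appendix D states neither the term's meaning nor any denominator, and it does not say how the partial follow-up of exited subjects counts in the two-year summaries. Nor does the device-arm reading make Appendix D complete. Subjects randomized to device but never attempted have no exit instruction and no implant date, and the randomization clock they had in 2.12 #3 was in the replaced text. Their schedule in 2.12.2 is not amended, so only the starting date is unstated, and nothing in the documents shows that any such subject exists.

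The step from loose wording to lost events does not stand. It needs a reading that contradicts the exit sentence, sets aside the unamended endpoint definition in 1.4.2.1, and narrows a promise about collected safety data that carries no restriction. The severalfold change also needs most or all of a handful of events to fall among a few non-recipients. It rests on a crossover share standing in for non-implantation and on a performance goal standing in for an event rate.

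**Conclusion.** No change to the plan follows. This is missing detail that the analysts can fill sensibly: Appendix D does not define 'device subjects', but its own sentences and the unamended sections point to the device arm, so serious events that prevented implantation are reported. What remains is to show denominators (randomized, attempted, implanted, exited) and to label any recipients-only figure as such, which is ordinary practice in a final report.

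The consequence is small in any case. Appendix D withdraws the hypotheses and the labeling claims, so no test, decision or claim depends on the denominator. In the illustration the whole-arm acute rate is 4.6%, against 0 to 5.3% for recipients only across 2 to 8 non-recipients, with wide and overlapping intervals. No effect on actual results is shown.

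The conclusion assumes that the report covers the device arm, as the text indicates, and counts events recorded before exit. A report limited to recipients without saying so would depart from the plan as written.
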